8.5.4 ECOG performance

ECOG performance grade (0,1,2,3,4) will be presented in shift tables from baseline to each scheduled visit by visit and treatment group. Significant shift from baseline will be tested using Bowker's test.

Data will be summarized in the following table.

- *Table. Shift Table on ECOG grade – Safety Set*

9. SUBGROUP ANALYSIS

Subgroup analyses will be conducted on randomization stratification factors. In the event of any randomization errors, the correct classification of the factor will be used.;

1. Geographic region (Asia vs. North America/Europe)
2. Disease measurability (Measurable vs. Non-measurable)
3. Prior ramucirumab treatment (Yes vs. No)
4. Treatment therapy line (3rd vs. ≥ 4th)

In addition, a subgroup analysis will also be conducted for treatment therapy line comparing 3rd vs 4th vs. 5th. The 5th line subjects will be identified based on recorded prior lines of therapy as this was not a stratification factor.

The analysis for the efficacy endpoints OS, PFS, ORR, DCR using ITT population will be repeated for each subgroup. Descriptive statistics by visit for the efficacy endpoint will also be produced by subgroup. Note that subgroup analysis will be performed if there are sufficient subjects within a subgroup for statistical analysis. Otherwise, only descriptive statistics will be displayed.

The study has been sized to provide adequate power for the primary analysis. The subgroup analyses may not necessarily reach statistical significance at the 5% level. P-values and 95% confidence intervals will be provided but will not be considered inferential. However, a consistency of treatment effect is expected across the primary and all subgroup analyses. Subgroup analyses are mainly to demonstrate trend and assess internal consistency of any treatment benefit and/or safety signal. Only the analyses that provide meaningful information will be presented for the CSR.

Additional subgroup analyses will be performed to assess the consistency of treatment benefit per the primary outcome of overall survival. A forest plot displaying the hazard ratio and its 95% confidence interval will be generated for all the subgroups, including the four stratification groups mentioned above:

1. Treatment therapy line (3rd vs. 4th vs. 5th)
2. Age category (<65 vs. ≥ 65)
3. ECOG status (0 vs. 1 at baseline)
4. Race (white, Asian, black, and others)
5. Sex (male vs. female)
6. Previous gastrectomy (Yes vs. No)
7. Number of organs with metastases (<2 vs. ≥ 2)
8. Liver metastases (Yes vs. No)

Data will be summarized in the following tables.

- Table. Overall Survival [Asia] – ITT
- Table. Overall Survival [North America/Europe] – ITT
- Table. Overall Survival [Measurable] – ITT
- Table. Overall Survival [Non-measurable] – ITT
- Table. Overall Survival [Prior ramucirumab] – ITT
- Table. Overall Survival [No prior ramucirumab] – ITT
- Table. Overall Survival [3rd line therapy] – ITT
- Table. Overall Survival [\geq 4th line therapy] – ITT
- Table. Overall Survival [\geq 5th line therapy] – ITT
- Table. Overall Survival [< 65 ages] – ITT
- Table. Overall Survival [\geq 65 ages] – ITT
- Table. Overall Survival [ECOG status at baseline: 0] – ITT
- Table. Overall Survival [ECOG status at baseline: 1] – ITT
- Table. Overall Survival [White] – ITT
- Table. Overall Survival [Asian] – ITT
- Table. Overall Survival [Black] – ITT
- Table. Overall Survival [Others] – ITT
- Table. Overall Survival [Male] – ITT
- Table. Overall Survival [Female] – ITT
- Table. Overall Survival [Previous gastrectomy] – ITT
- Table. Overall Survival [Non-previous gastrectomy] – ITT
- Table. Overall Survival [Organs with metastases: <2] – ITT
- Table. Overall Survival [Organs with metastases: \geq 2] – ITT
- Table. Overall Survival [Liver metastases] – ITT
- Table. Overall Survival [Non-liver metastases] – ITT

- Table. Progression Free Survival [Asia] – ITT
- Table. Progression Free Survival [North America/Europe] – ITT
- Table. Progression Free Survival [Measurable] – ITT
- Table. Progression Free Survival [Non-measurable] – ITT
- Table. Progression Free Survival [Prior ramucirumab] – ITT
- Table. Progression Free Survival [No prior ramucirumab] – ITT
- Table. Progression Free Survival [3rd line therapy] – ITT
- Table. Progression Free Survival [\geq 4th line therapy] – ITT
- Table. Progression Free Survival [4th line therapy] – ITT
- Table. Progression Free Survival [5th line therapy] – ITT

- Table. Progression Free Survival [< 65 ages] – ITT
- Table. Progression Free Survival [≥ 65 ages] – ITT
- Table. Progression Free Survival [ECOG status at baseline: 0] – ITT
- Table. Progression Free Survival [ECOG status at baseline: 1] – ITT
- Table. Progression Free Survival [White] – ITT
- Table. Progression Free Survival [Asian] – ITT
- Table. Progression Free Survival [Black] – ITT
- Table. Progression Free Survival [Others] – ITT
- Table. Progression Free Survival [Male] – ITT
- Table. Progression Free Survival [Female] – ITT
- Table. Progression Free Survival [Previous gastrectomy] – ITT
- Table. Progression Free Survival [Non-previous gastrectomy] – ITT
- Table. Progression Free Survival [Organs with metastases: <2] – ITT
- Table. Progression Free Survival [Organs with metastases: ≥2] – ITT
- Table. Progression Free Survival [Liver metastases] – ITT
- Table. Progression Free Survival [Non-liver metastases] – ITT

- Table. Objective Response Rate [Asia] – ITT
- Table. Objective Response Rate [North America/Europe] – ITT
- Table. Objective Response Rate [Measurable] – ITT
- Table. Objective Response Rate [Non-measurable] – ITT
- Table. Objective Response Rate [Prior ramucirumab] – ITT
- Table. Objective Response Rate [No prior ramucirumab] – ITT
- Table. Objective Response Rate [3rd line therapy] – ITT
- Table. Objective Response Rate [≥ 4th line therapy] – ITT
- Table. Objective Response Rate vival [4th line therapy] – ITT
- Table. Objective Response Rate [5th line therapy] – ITT
- Table. Objective Response Rate [< 65 ages] – ITT
- Table. Objective Response Rate [≥ 65 ages] – ITT
- Table. Objective Response Rate [ECOG status at baseline: 0] – ITT
- Table. Objective Response Rate [ECOG status at baseline: 1] – ITT
- Table. Objective Response Rate [White] – ITT
- Table. Objective Response Rate [Asian] – ITT
- Table. Objective Response Rate [Black] – ITT
- Table. Objective Response Rate [Others] – ITT
- Table. Objective Response Rate [Male] – ITT
- Table. Objective Response Rate [Female] – ITT
- Table. Objective Response Rate [Previous gastrectomy] – ITT
- Table. Objective Response Rate [Non-previous gastrectomy] – ITT

- Table. Objective Response Rate [Organs with metastases: <2] – ITT
- Table. Objective Response Rate [Organs with metastases: ≥2] – ITT
- Table. Objective Response Rate [Liver metastases] – ITT
- Table. Objective Response Rate [Non-liver metastases] – ITT

- Table. Disease Control Rate [Asia] – ITT
- Table. Disease Control Rate [North America/Europe] – ITT
- Table. Disease Control Rate [Measurable] – ITT
- Table. Disease Control Rate [Non-measurable] – ITT
- Table. Disease Control Rate [Prior ramucirumab] – ITT
- Table. Disease Control Rate [No prior ramucirumab] – ITT
- Table. Disease Control Rate [3rd line therapy] – ITT
- Table. Disease Control Rate [≥ 4th line therapy] – ITT
- Table. Disease Control Rate [4th line therapy] – ITT
- Table. Disease Control Rate [5th line therapy] – ITT
- Table. Disease Control Rate [< 65 ages] – ITT
- Table. Disease Control Rate [≥ 65 ages] – ITT
- Table. Disease Control Rate [ECOG status at baseline: 0] – ITT
- Table. Disease Control Rate [ECOG status at baseline: 1] – ITT
- Table. Disease Control Rate [White] – ITT
- Table. Disease Control Rate [Asian] – ITT
- Table. Disease Control Rate [Black] – ITT
- Table. Disease Control Rate [Others] – ITT
- Table. Disease Control Rate [Male] – ITT
- Table. Disease Control Rate [Female] – ITT
- Table. Disease Control Rate [Previous gastrectomy] – ITT
- Table. Disease Control Rate [Non-previous gastrectomy] – ITT
- Table. Disease Control Rate [Organs with metastases: <2] – ITT
- Table. Disease Control Rate [Organs with metastases: ≥2] – ITT
- Table. Disease Control Rate [Liver metastases] – ITT
- Table. Disease Control Rate [Non-liver metastases] – ITT

- Figure. Forest plot of Hazard Ratio for all subgroups – ITT

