7.5.2 Primary Efficacy Analysis

- Overall Survival (OS): Time from randomization to death. Subjects alive or lost to follow-up are censored at the date the subject was last known to be alive.

The primary efficacy endpoint (OS) will be analyzed using ITT, FAS and PPS. The primary efficacy analysis will be conducted using the ITT set. The final analysis will be conducted when approximately 325 events are observed.

The comparison of OS between the two treatment groups will be performed with a logrank test stratified on the randomization stratification variables Geographic region (Asia vs. North America/Europe), Prior

ramucirumab treatment (Yes vs. No), and Treatment therapy line (3rd vs. ≥ 4th) at the two-sided alpha=0.05 level of significance.

In order to estimate the hazard ratio, a Cox proportional hazards regression model will be fitted with treatment group as a factor and the randomization stratification variables [Geographic region (Asia vs. North America/Europe), Disease measurability (measurable vs. nonmeasurable), Prior ramucirumab treatment (Yes vs. No), and Treatment therapy line (3rd vs. ≥ 4th)] as covariates. The hazard ratio and its 95% confidence interval will be presented.

Kaplan-Meier estimates will be calculated for each treatment group to construct the survival curve. The median overall survival and its 95% CI (based on Greenwood formula) will be presented. The primary endpoints will also be analyzed using the FAS and PPS.

Data will be summarized in the following tables and figures.

-Table. Overall Survival – ITT

-Table. Overall Survival – FAS

-Table. Overall Survival – PPS

-Figure. Kaplan Meier Plot for Overall Survival – ITT

-Figure. Kaplan Meier Plot for Overall Survival – FAS

-Figure. Kaplan Meier Plot for Overall Survival – PPS

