7.5.3 Key Secondary Efficacy Analysis

The key secondary efficacy endpoints (PFS, ORR) will be analyzed using ITT, FAS and PPS. The key secondary efficacy analyses will be conducted using the ITT set.

- Progression Free Survival (PFS): Time from randomization to either documented radiological progression (determined by the central imaging analysis facility) or death from any cause. Subjects alive and free of progression are censored at the last tumor assessment date when alive and free of progression were known.
- Objective Response Rate (ORR): Percentage of subjects with a Best Overall Response (determined by the central imaging analysis facility) of Complete Response (CR) or Partial Response (PR).

PFS will be analyzed using the same statistical methods that are used in the primary efficacy analysis of OS.

ORR will be analyzed using the Cochran-Mantel-Haenszel test stratified by the randomization stratification factors Geographic region (Asia vs. North America/Europe), Prior ramucirumab treatment (Yes vs. No), and Treatment therapy line (3rd vs. ≥ 4th). For the ORR, the frequency and percentage (with 95% CI) of subjects will also be provided.

Data will be summarized in the following tables and figures.

-Table. Progression Free Survival [Independent Central Review] – ITT

-Table. Progression Free Survival [Independent Central Review] – FAS

-Table. Progression Free Survival [Independent Central Review] – PPS

-Figure. Kaplan Meier Plot for Progression Free Survival [Independent Central Review] - ITT

-Figure. Kaplan Meier Plot for Progression Free Survival [Independent Central Review] - FAS

-Figure. Kaplan Meier Plot for Progression Free Survival [Independent Central Review] – PPS

-Table. Objective Response Rate [Independent Central Review] – ITT

-Table. Objective Response Rate [Independent Central Review] – FAS

-Table. Objective Response Rate [Independent Central Review] – PPS

-Table. Progression Free Survival - [Investigator Review] – ITT

-Table. Progression Free Survival - [Investigator Review] – FAS

-Table. Progression Free Survival - [Investigator Review] – PPS

-Table. Objective Response Rate - [Investigator Review] – ITT

-Table. Objective Response Rate - [Investigator Review] – FAS

-Table. Objective Response Rate - [Investigator Review] – PPS

- List. Time to Event Parameters by Subjects – ITT Set

- List. Objective Response by Subject – ITT Set

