Section 8.3.4 p.77	Section 7.5.2 p.29-30	“For the ORR (CR or PR), ...Response in both treatment groups will be compared with the Cochran-Mantel-Haenszel test stratified by the randomization stratification factors.”	“ORR will be analyzed using the Cochran-Mantel-Haenszel test stratified by the randomization stratification factors Geographic region (Asia vs. North America/Europe) , Prior ramucirumab treatment (Yes vs. No) , and Treatment therapy line (3rd vs. ≥ 4th) .”	Due to the occurrence of several very small strata for non-measurable subjects, it is not meaningful to conduct stratified analyses using all four randomization stratification variables. The measurable vs. non-measurable stratification criteria will not be utilized in all stratified analyses.
Section 8.3.4 p.82	Section 5.1.2 p.19	Entire table: Table 8. PFS censoring rule	Entire table: Table 8. PFS censoring rule . Subjects alive and free of progression are censored at the last tumor assessment date when alive and free of progression were known.”	Scenarios in Table 8 in the protocol is redundant and not entirely accurate, so the entire table is removed and replaced by the censoring guideline described in this SAP. Specifically, death for any cause should always be a PFS event.

[figure not shown]
* Note: For purposes of this SAP, Rivoceranib will be used as the nonproprietary name throughout the document. Apatinib was formerly used in the protocol. In addition, grammatical and typographical changes are not included in the table.

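### SAP 9 carries the primary strata and covariates unchanged into every subgroup; in the non-measurable subgroup these are the strata SAP 13 rejects as too small

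*SAP*

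**What the plan says.** SAP 9 sets the rule: "The analysis for the efficacy endpoints OS, PFS, ORR, DCR using ITT population will be repeated for each subgroup". The analysis to be repeated is defined elsewhere:

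- OS and PFS (SAP 7.5.2, 7.5.3): a "logrank test stratified on the randomization stratification variables Geographic region (Asia vs. North America/Europe), Prior" ramucirumab and therapy line, which gives up to 8 strata. Measurability is not a stratifier.
- Hazard ratio (SAP 7.5.2): "a Cox proportional hazards regression model will be fitted with treatment group as a factor and the randomization stratification variables" as covariates. Here all four factors are listed, including measurability.
- ORR, and DCR by reference: "Cochran-Mantel-Haenszel test stratified by the randomization stratification factors Geographic region (Asia vs. North America/Europe"), with the same three factors.

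SAP 13 explains why measurability was removed from the strata: "Due to the occurrence of several very small strata for non-measurable subjects, it is not meaningful to conduct stratified analyses" on all four factors. It gives no counts.

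SAP 9 has two safeguards. The first is "Note that subgroup analysis will be performed if there are sufficient subjects within a subgroup for statistical analysis", with descriptive statistics otherwise; no number is attached. The second is "P-values and 95% confidence intervals will be provided but will not be considered inferential". Later in the same section, "A forest plot displaying the hazard ratio and its 95% confidence interval will be generated for all the subgroups". The table list includes non-measurable disease for OS, PFS, ORR and DCR, and also fifth line, Black and Others.

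**The concern.** Nothing in Section 9 drops a stratum or covariate, or the factor that defines the subgroup. Two problems follow.

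First, there is an internal conflict. Restricting to non-measurable subjects and stratifying by the other three factors produces exactly the non-measurable cells that SAP 13 found too small for a meaningful stratified analysis.

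Second, there is an efficiency problem in any small subgroup. A stratum with one arm contributes nothing to a stratified log-rank or CMH test. A Cox model with treatment and three or four covariates on a handful of deaths gives unstable hazard ratios and intervals that are too narrow.

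Section 9 wants the subgroups to show whether the treatment effect is consistent. Avoidable noise works against that, because it produces chance reversals on the forest plot.

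**Working it through.** **Design figures first.** Inputs: HR 0.72 (SAP 12.2), 2:1 allocation, two-sided 0.05, about 80% power and 325 events in 413 subjects (SAP 13), about 459 subjects (Protocol synopsis). Schoenfeld: events = (1.960 + 0.842)² / [(2/3)(1/3)(ln 0.72)²] = 7.85 / (0.2222 × 0.1079) = 328, against 325 stated. Power at 325 events is 79.7%. With an assumed 10% dropout, 413 / 0.90 = 459. Expected death fraction: 325 / 459 = 71%.

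**Subgroup sizes.** The documents give none. A subgroup of 5% of 459 is assumed for illustration: 23 subjects and about 23 × 0.71 = 16 deaths. A 10% subgroup is 46.

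**Why strata cost information.** Log-rank information sums, over strata and death times, a term proportional to n₁n₀/n² among those at risk. It is zero once one arm is empty. With 23 subjects in 8 cells the mean is 2.9 per cell. Under simple 2:1 allocation, a cell of three is one-arm with probability (2/3)³ + (1/3)³ = 9/27 = 1/3.

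**Simulations.** True HR was 0.72.

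- Blocked: assumed permuted blocks of 3 within cells; factor splits 25/75, 40/60, 40/60; 65 to 71% deaths; three covariates.
- Simple: simple 2:1 allocation; factor prevalences 25, 40, 35 and 10%; about 65% deaths; three strata factors and four covariates; up to 600 runs per size; non-convergent fits dropped.

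The Cox columns give the variance of the log HR with covariates divided by the variance with treatment only.

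| Subgroup n | Allocation | Log-rank information kept | Cox ratio, empirical | Cox ratio, model-based |
|---|---|---|---|---|
| 23 | blocked | 72–77% | 1.5–2.1 | 1.2 |
| 46 | blocked | 83–88% | 1.2–1.3 | 1.06 |
| 230 | blocked | 98% | – | – |
| 20 | simple | 1/1.65 = 61% | 2.2 | 1.43 |
| 40 | simple | 1/1.34 = 75% | 1.4 | 1.17 |
| 100 | simple | 1/1.14 = 88% | 1.13 | 1.06 |
| 200 | simple | 1/1.07 = 93% | 1.06 | 1.03 |

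Sources of the blocked figures:

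- Information: 2.49 / 3.21 = 77% at 23, 5.79 / 6.57 = 88% at 46, 33.1 / 33.8 = 98% at 230. A separate run gave 72% and 83% at the two smaller sizes.
- Cox: (0.80 / 0.55)² = 2.1 at 23 and (0.42 / 0.37)² = 1.29 at 46. Runs that dropped divergent fits gave 1.5 and 1.2.
- Coverage of the 95% interval: 92% at 23 and 93% at 46, against 95% for treatment only.

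The empirical ratio exceeds the model-based ratio at small sizes, so the reported standard errors understate the real spread. In the simple-allocation runs, 136 of 600 had a non-converging fit at n = 20 and 248 of 600 at n = 16.

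Blocking is the more relevant case for the non-measurable subgroup, because measurability is a randomization factor. Simple allocation is closer for race or fifth line, which are not.

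**Response endpoints.** The earlier Chinese phase III trial had an ORR of 2.84% v 0% (Protocol 1.2). If that held here, 459 × 2/3 = 306 treated subjects would give 306 × 0.0284 ≈ 9 responders. A subgroup of 23, with about 15 on active drug, would expect 15 × 0.0284 = 0.4. The chance of none is 0.9716¹⁵ = 65%. An eight-cell CMH test would then have little to compare.

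**The case against.** A reader might infer that the rejected strata come back in every subgroup. They do not. SAP 13 takes measurability out of all stratified analyses, so those particular cells reappear only among non-measurable subjects. Sparse cells by race or line are different cells. For fifth line, the line factor is constant, which leaves at most 4 log-rank strata, not 8.

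A reader might also infer that stratification inflates the hazard ratio variance. The hazard ratio comes from a Cox model with covariates; stratification affects the log-rank and CMH tests. SAP 13's remark is about stratified analyses and does not speak to the Cox model.

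A doubling of variance is not a property of the plan either. It needs a subgroup of about 20, which the documents do not describe, and it depends on how near-divergent fits are handled.

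The safeguards carry weight. Very small subgroups may fall to descriptive statistics, p-values and intervals are declared non-inferential, and only informative analyses go into the study report. But the sufficiency clause looks at subgroup size, not stratum size, and gives no number. The forest plot is called for in all subgroups.

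Section 9 also does not say in words that subgroup tests are stratified. SAP 14 has separate headings for a log-rank test and a stratified one. Their content is redacted, so an unstratified subgroup test cannot be excluded. Still, the visible text points to repeating the stratified analysis.

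Finally, a treatment-only model targets a marginal hazard ratio. With assumed prognostic effects of 0.5 on the log scale per factor, its mean log HR was −0.30 against a conditional −0.33. That shift is small beside the sampling error, and treatment-only Cox still had the lower error at 46 subjects and above.

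**Conclusion.** The concern holds in limited form. As written, SAP 9 sends the non-measurable subgroup through strata that SAP 13 calls too small, and it gives other small subgroups more strata and covariates than they can support. The conflict with SAP 13 follows from the text alone.

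The size rests on assumed subgroup sizes, factor splits and allocation within cells. With blocked allocation, the stratified log-rank loses about a quarter of its information at 23 subjects (23 to 28%) and 12 to 17% at 46; simple allocation loses more. The adjusted Cox variance is about 20 to 30% higher at 46 and up to about double near 20, with coverage around 92 to 93%. At 200 or more the loss is small.

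It would be wrong to read this as a threat to the trial's conclusions. The primary test, the fixed testing sequence and the type I error are untouched. What is affected is the precision and calibration of exploratory subgroup tables and the forest plot.

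**What to change.** In SAP 9, replace the repeat-the-analysis sentence with three statements:

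- Subgroup hazard ratios and confidence intervals come from an unstratified Cox model with treatment only, fitted within each subgroup, with an unstratified log-rank test.
- Subgroup ORR and DCR are given as unstratified differences with exact confidence intervals.
- A pre-set minimum number of events replaces the sufficiency clause and also governs entry to the forest plot. It can be set from counts pooled over arms, before unblinding.

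A single ITT model with a treatment-by-subgroup term is a possible alternative. If it is stratified by the three factors, it cannot estimate the subgroup main effect when the subgroup is itself one of them, so it would need more careful wording.

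The cost is a short SAP edit and simpler programming. The downside is that subgroup estimates become marginal and are not adjusted in the same way as the primary model; a footnote to the forest plot should say so.

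### SAP section 9 lets an undefined test of meaningfulness decide which subgroup analyses reach the study report, leaving mainly the 78 PFS, ORR and DCR tables open to selective reporting

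*SAP*

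**What the plan says.** SAP section 9 sets out the scope first: "The analysis for the efficacy endpoints OS, PFS, ORR, DCR using ITT population will be repeated for each subgroup". It then adds further factors to assess the consistency of the OS benefit. The closing list, introduced by "Data will be summarized in the following tables", carries tables for nearly all of these subgroups on all four endpoints.

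On interpretation it says "P-values and 95% confidence intervals will be provided but will not be considered inferential", then "However, a consistency of treatment effect is expected across the primary and all subgroup analyses", and gives the aim: "Subgroup analyses are mainly to demonstrate trend and assess internal consistency of any treatment benefit and/or safety signal". The next sentence is the reporting rule: "Only the analyses that provide meaningful information will be presented for the CSR". The SAP does not define *meaningful*, and does not say who judges it or when.

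Two other statements in the section bear on this:

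- Where a subgroup has too few subjects, only descriptive statistics are to be displayed. No number defines too few.
- For OS: "A forest plot displaying the hazard ratio and its 95% confidence interval will be generated for all the subgroups, including the four stratification groups mentioned" earlier in the section. The figure also appears at the end of the output list.

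**The concern.** The section exists to check whether the effect is consistent. A check of that kind is informative only if what is shown does not depend on what was found. Here the rule depends on content, has no stated criterion, and stands beside a declared expectation that the results will agree. If the selection is made after results by arm are known, the reported set can look more consistent than the data are, and a reader of the study report cannot tell whether that has happened.

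Sparse data do not explain the rule. Small subgroups already have a fallback, and under it something is still displayed. The sentence on meaningful information goes further and permits an analysis to be left out.

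What is at stake is the credibility of the descriptive subgroup results, above all for PFS and ORR, the two key secondary endpoints, and for DCR. The confirmatory tests are not at stake.

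**Working it through.** **1. Count of tables (output list, SAP section 9).**

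- Four stratification factors, two levels each: 8 tables per endpoint.
- Age 2, ECOG 2, race 4, sex 2, gastrectomy 2, number of organs 2, liver metastases 2: 16 per endpoint.
- Extra therapy-line tables: OS has 1 (5th line or later); PFS, ORR and DCR have 2 each (4th and 5th).
- OS: 8 + 16 + 1 = 25. PFS, ORR and DCR: 8 + 16 + 2 = 26 each.
- Total: 25 + 3 × 26 = 103, of which 3 × 26 = 78 are not OS.

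**2. What is protected.** The forest plot shows a hazard ratio and interval for OS only. No comparable all-subgroup display is promised for the 78 other tables. The plot is to be *generated*; the SAP does not say whether the sentence on meaningful information also governs its place in the study report.

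**3. The plan's own event figure, to fix the formula.** Inputs: hazard ratio 0.72 (SAP 12.2), two-sided 5% (SAP 7.5.2), 2:1 allocation (SAP 3.4), 325 deaths (SAP 7.5.2), about 80% power (SAP 13). With 2:1 allocation the Schoenfeld information per death is (2/3)(1/3) = 2/9.

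- Deaths for 80% power: (1.960 + 0.842)² / [(2/9)(ln 0.72)²] = 327.3, so 328, against 325 stated.
- Power at 325 deaths: Φ(0.3285 × √(325 × 2/9) − 1.960) = Φ(2.792 − 1.960) = 0.797.

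The formula reproduces the plan.

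**4. Chance of an apparently reversed OS result when the true ratio is 0.72 in everyone.** P(observed HR > 1) = Φ(ln 0.72 × √(d × 2/9)), with d deaths in the subgroup. The documents give no subgroup shares, so d is an assumption.

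| Deaths d | About what share of 325 | P(HR > 1) |
|---|---|---|
| 162.5 | 50% | Φ(−1.974) = 2.4% |
| 81 | 25% | Φ(−1.394) = 8.2% |
| 26 | 8% | Φ(−0.790) = 21.5% |

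**5. Chance of at least one reversed OS subgroup.** This depends on the assumed shares. If ten independent factors each split the deaths in half, write m for the overall log hazard ratio divided by its standard error, so m ~ N(−2.792, 1). The two halves of a factor are then m ± e with e ~ N(0, 1). The probability that at least one of the 20 halves exceeds zero is the average over m of 1 − [1 − 2Φ(m)]¹⁰ for m < 0, and 1 for m ≥ 0. Numerical integration gives 21%. Simulations with unequal shares and small groups gave values up to about 63%. A fair range is roughly 20–63%.

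Steps 4 and 5 concern OS, the endpoint that the forest plot largely protects. They show that awkward subgroup results are to be expected by chance; they do not measure how much could be omitted. The gap itself is the count in steps 1 and 2.

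**The case against.** **The forest plot covers OS.** An OS subgroup with a ratio above 1 would appear there even if its table were dropped. This stands, and it is why the point is confined mainly to the 78 other tables and the OS table detail. The open question is whether the plot itself is subject to the filter.

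**The sentence may be aimed at sparse tables.** The earlier phase III trial had an ORR of 2.84% against 0% (Protocol 1.2), so many of the 26 ORR subgroup tables may hold very few responders. This is a plausible motive. But the section already handles small groups by displaying descriptive statistics, and sparseness can be expressed as a number fixed in advance.

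**A reader might infer that the sponsor intends to drop unfavourable results after unblinding.** The documents do not support that. The sentence names no direction, decision-maker or time. It permits such a choice; it does not announce one.

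**A reader might also infer that false positive claims become more likely.** They do not. Subgroup p-values are declared non-inferential, and confirmatory testing rests on the fixed OS, PFS, ORR sequence in the ITT set (SAP 7.5.1). Subject-level listings of demographics (SAP 7.1), time-to-event data and objective response (SAP 7.5.3) would also let a regulator rebuild many omitted subgroups.

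**The absence of an interaction test is a matter of preference.** Largely agreed. With 325 deaths split evenly, and ratios of 0.72 in one half and 1.0 in the other, the standard error of the difference in log ratios is √(2 / (162.5 × 2/9)) = 0.235. Power is Φ(0.3285/0.235 − 1.960), about 29%, so a non-significant result would not establish consistency. The visible text mentions no such test, but the Cox code is blacked out and the mock-up tables are only named, so its absence cannot be confirmed.

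**Conclusion.** The concern holds in limited form. SAP section 9 contains a stated rule that allows selection of subgroup results for the study report without a result-independent criterion, a decision-maker or a date. It reaches the 78 PFS, ORR and DCR tables and the detail in the 25 OS tables. It reaches the OS hazard ratios only if the sentence also governs where the forest plot appears, which the SAP leaves open.

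The consequence is selective reporting of descriptive results. Type I error for OS, PFS and ORR is untouched. The OS figures are for scale and rest on a uniform ratio of 0.72 and assumed death counts; the chance of at least one reversed subgroup should be given only as a range. This should be corrected because the correction is easy and the section cannot do its job otherwise; it does not threaten the primary conclusion.

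**What to change.** - Delete the sentence on meaningful information. State that every subgroup output listed in SAP section 9, including the OS forest plot, will be presented in the study report or its appendices.
- If a minimum size is wanted, fix it before unblinding, as a number that does not depend on results: events for OS and PFS, subjects for ORR and DCR. Below it, show descriptive statistics instead of omitting the subgroup. This also replaces the undefined notion of sufficient subjects.
- Optionally, print a descriptive treatment-by-subgroup interaction estimate or p-value for each factor beside the forest plot, with a note on its low power.
- Reconcile the OS table list, which has a table for 5th line or later but none for 4th line, with the planned comparison of 3rd, 4th and 5th line and with the PFS, ORR and DCR lists.

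The cost is a few lines of SAP wording and one corrected list entry. The tables are already planned; the optional interaction adds one model term per factor.
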